11.1.1 Source

The ETBX vaccines will be supplied by the manufacturer, Etubics Corporation, through a Cooperative Research and Development Agreement (CRADA). The manufacturing department of Etubics will supply each vaccine in 2-mL single-dose vials. Each single-dose vial contains a sterile, clear suspension of the ETBX vaccine at 5×10^{11} VP per 1 mL intended for single dose administration and contains ARM formulation buffer (20 mM TRIS, 25 mM NaCl, 2.5% glycerol, pH 8.0).

Upon receipt of the investigational product, the Investigator or delegated designee will verify that an appropriate shipping temperature was maintained, conduct an inventory, and sign the drug receipt form and send a scanned copy to the Sponsor contact as designated on the form. If a temperature excursion occurs, the Sponsor should be notified immediately, and the investigational product must be quarantined and maintained under the correct storage conditions until further instructions are provided by the Sponsor. The temperature excursion form will need to be completed and returned to the Sponsor. The original drug receipt form and packing slip must be retained in the Investigator's pharmacy records.

11.1.2 Toxicity

The safety of immunizations (injections) with the ETBX-011, ETBX-051, ETBX-061 vaccines has not been established and will be determined in this phase I clinical trial.

A Phase I/II clinical trial of ETBX-011 (Ad5 [E1-, E2b-]-CEA(6D)) (IND#14325) that expresses the tumor-associated antigen carcinoembryonic antigen (CEA) has been performed. A summary of the study results on the clinical trial is presented below.

Schedule, Dosing, and Safety of ETBX-011: The primary objective of the Phase I/II dosing trial was to assess safety and a secondary objective was to evaluate CEA-specific immune responses to CEA and to obtain preliminary data on response rate. The study was performed under an FDA-approved IND (IND14325) and registered at ClinicalTrials.gov (NCT01147965). Participants were recruited from oncology clinics at Duke University Medical Center and Medical Oncology Associates, Spokane, WA and provided informed consent that was approved by IRB's. Patients with a histological confirmed diagnosis of metastatic malignancy who were previously treated with standard therapy known to have a possible survival benefit were enrolled into the study. For this study, the carcinoma must have had over expression of CEA as defined by immunohistochemical staining (at least 50% of the tumor with at least moderate intensity of staining) or a carcinoma known to be universally CEA positive *i.e.* colorectal adenocarcinoma). Patients were not treated until 4 or more weeks after any prior chemotherapy or radiation therapy. They could not have a history of autoimmune disease, serious intercurrent chronic or acute illness, active hepatitis, serologic evidence for HIV infection, or be receiving steroid or immunosuppressive therapy. All patients were ≥ 21 years old and had a Karnofsky Performance Score of 70% or higher and a life expectancy of at least 3 months. Pregnant women and nursing mothers were excluded. Dose Limiting Toxicities (DLTs) were defined as any Grade 3 or 4 immediate hypersensitivity reactions, Grade 3 or 4 fever that may possibly be associated with the immunization, Grade ≥ 2 autoimmune events except for vitiligo or fever for less than 2 days and less than 101.5 °F, Grade ≥ 2 allergic

reactions (Grade 2 is defined as generalized urticaria as defined by NCI Common Terminology Criteria for Adverse Events (CTCAE version 5.0), or Grade ≥ 3 non-hematologic toxicity. The Ad5 [E1-, E2b-]-CEA(6D) injections were given subcutaneously in the same thigh. The doses were administered every 3 weeks for 3 treatments as follows: Cohort 1 (3 patients) 10^9 VP in 0.5 ml; Cohort 2 (3 patients): 10^{10} VP; Cohort 3 (6 patients) 10^{11} VP. Following establishment of safety in Phase I, 12 additional patients were entered into a Phase II using the 10^{11} VP/dose. To evaluate a higher dose, 6 additional patients (cohort 5) received 5×10^{11} VP/dose.

Patient Demographics: One patient with CEA expressing bladder and one patient with lung carcinoma was enrolled. Thirty-two patients, median age 57.5 (range 38-77) with metastatic colorectal cancer, who had failed a median of three prior chemotherapeutic regimens (range: 2–5), had a median performance status of 90% (range 70-100%), and had a median of three sites of metastatic disease (range 1-5), were enrolled. The majority was able to receive all three immunizations. Five patients who stopped immunizations early did so due to significant disease progression. The colorectal adenocarcinoma patient demographics compares favorably with previously published studies of patients with chemotherapy-refractory colorectal cancer [44-46].

Adverse Effects: A total of 94 immunization treatments were administered to all patients. There was no dose limiting toxicity and no serious adverse events that resulted in treatment discontinuation at any dose level. The most common toxicity was a self-limited, injection site reaction. Other reactions that occurred at a low frequency include fever, flu-like symptoms, anorexia, chills, nausea, and headache. These symptoms were also self-limiting and did not require intervention other than symptomatic measures such as acetaminophen. There were no SAE associated with immunizations. A summary of the adverse events reported on 34 patients treated and evaluated for safety are presented below.

Adverse Events: $\geq 5\%$ Frequency Based on Incidence of Total Treatments

Adverse Events as of 07/31/12	# of Events	Unrelated/Unlikely	Possible	Probably/Definite	Incidence % (based on 94 total treatments)
Injection Site Reaction	21	2		21	22.3
Flu-like symptoms	10	4	5	3	10.6
Fever	9	6	1	4	9.5
Fatigue	8	6	2		8.5
Shortness of Breath	6	6			6.3
Pain	6	4			6.3
Anorexia	5		1		5.3
Chills	5	5	1	4	5.3
Constipation	5	5			5.3
Edema	5	4			5.3
Nausea	5	4	1		5.3

Grade 3 and Grade 4 Adverse Events in \geq 2% of Patients*

Adverse Events	Number of Grade 3 (G3)	Number of Grade 4 (G4)	Percent (Based on 34 patients evaluated for safety)
Pain (all types)	2		5.6
Fatigue	1		2.9
Anemia	1		2.9
Pleural effusion	1		2.9
Alkaline Phosphatase Increase	1		2.9
Abdominal Bloating	1		2.9
Bowel obstruction	1		2.9
GI disorder	1		2.9
Acute renal failure	1		2.9

*Represents reported adverse events whether or not related to ETBX-011 vaccine

Of 34 total patients entered into the trial, 28 received all three treatments and the blood hematology, chemistry, and ANA values at week 0 (prior to first treatment) were compared with those obtained at week 9 (three weeks after the third treatment). There were no biologically significant changes in chemistry, hematology, or ANA values.

11.1.3 Formulation and Preparation

Each vaccine is supplied as a clear colorless liquid filled in a 2-mL amber vial at a concentration of 5×10^{11} total virus particles (VP) per 1.0 mL. Each vial is sealed with a rubber stopper and has a white flip off seal. End user of the product will need to flip the white plastic portion of the cap up/off with their thumb to expose the rubber stopper, and then puncture the stopper with an injection needle to withdraw the liquid. The rubber stopper is secured to the vial with an aluminum crimped seal.

11.1.4 Stability and Storage

Individual vials (in the desired number) of vaccine will be packaged in a cardboard box and will be shipped over dry ice by overnight courier with a temperature monitoring device included. Upon receipt, one will inspect contents of package for any noticeable damages or defects. Unpack the shipment contents and place the cardboard box containing vaccine vials into a freezer with a monitored temperature control. ETBX-011 vials should be stored at $-20 \pm 10^\circ\text{C}$; ETBX-051 and ETBX-061 vials should be stored at $\leq -60^\circ\text{C}$. Receiver must stop the temperature monitoring device by turning off the power switch (instructions for handling and operation of temperature monitoring device will be provided with the package).

11.1.5 ETBX Vaccine Dose Preparation and Administration

The dose of ETBX vaccine to be injected is 5×10^{11} VP per 1 mL. A dose level of 1×10^{11} VP per mL (dose level -1) is available for de-escalation. Prior to injection, the appropriate vial should be removed from the freezer and allowed to thaw at controlled room temperature ($20\text{--}25^\circ\text{C}$, $68\text{--}77^\circ\text{F}$) for at least 20 minutes and not more than 30 minutes, after which it should be kept at $2\text{--}8^\circ\text{C}$ (35--

46°F). The vaccine is stable in the vial for at least 8 hours after removal from the freezer when kept refrigerated at 2-8°C (35-46°F). Once the vaccine has been thawed, it must not be refrozen.

Each vial is sealed with a rubber stopper and has a white flip-off seal. The end user of the product will need to flip the white plastic portion of the cap up/off with their thumb to expose the rubber stopper and then puncture the stopper with an injection needle to withdraw the liquid. The rubber stopper is secured to the vial with an aluminum-crimped seal.

The thawed vial should be swirled and then, using aseptic technique, the pharmacist or pharmacist designee should withdraw the appropriate volume from the appropriate vial using an appropriately sized syringe.

The vaccine dose should be injected as soon as possible (i.e. within 1 hour) using a 1 to 1/2 inch, 20 to 25-gauge needle. If the vaccine cannot be injected within 1 hour, the syringe should be returned to the pharmacy and properly disposed in accordance with institutional policy and procedure, and disposition must be recorded on the investigational product accountability record.

11.1.5.1 Instructions for Dose Preparation – 5×10^{11} Virus Particles

Withdraw 1 mL of contents from the vial, prepare the injection site with alcohol, and administer to the subject by SC injection without any further manipulation (refer to the vial label for a description of the vial ETBX vaccine concentration).

11.1.5.2 Instructions for Dose Preparation – 1×10^{11} Virus Particles

Withdraw 0.2 mL of contents from the vial, prepare the injection site with alcohol, and administer to the subject by SC injection in the thigh without any further manipulation (refer to the vial label for a description of the vial ETBX vaccine concentration).

11.1.5.3 Administration

Each of the three ETBX vaccines will be administered on Weeks 0, 3, and 6 followed by bi-monthly booster vaccines for up to a year. All study drug administration treatments should occur within ± 7 days of the planned visit date.

ETBX-011 will be administered by subcutaneous injection in the upper arm after preparation of the site with alcohol. A 1 to ½ inch, 20- to 25- gauge needle should be used for administration.

ETBX-051 will be administered by subcutaneous injection in the anterolateral upper thigh after preparation of the site with alcohol. A 1 to ½ inch, 20- to 25- gauge needle should be used for administration. It is preferred to administer ETBX-051 and ETBX-061 in separate thighs. However, if administered in the same thigh, injection sites should be separated by at least 5 cm.

ETBX-061 will be administered by subcutaneous injection in the anterolateral upper thigh after preparation of the site with alcohol. A 1 to ½ inch, 20- to 25- gauge needle should be used for administration. It is preferred to administer ETBX-051 and ETBX-061 in separate thighs. However, if administered in the same thigh, injections sites should be separated by at least 5 cm.

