3.1.1 Dose Limiting Toxicity

For the purposes of dose escalation a dose limiting toxicity (DLT) is defined as:

- Any Grade 3 or greater toxicity that is possibly related to the vaccine and as defined by Common Terminology Criteria for Adverse Events (CTCAE) Version 5.0 with the exception of transient (≤ 24 hours) Grade 3 flu-like symptoms or fever, which is controlled with medical management or transient (≤ 24 hours) Grade 3 fatigue, skin reactions or rash, headache, nausea, emesis that resolves to Grade ≤ 1 or asymptomatic grade 3 amylase/lipase elevation. For purposes of dose escalation the DLT evaluation period will be for 3 weeks following the first dose of drug.

Subjects experiencing a DLT will be removed from protocol therapy.

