3.3 DOSE DELAY OR DISCONTINUATION

Applies to events occurring outside of the DLT evaluation period

- Patients must have recovered to \leq grade 2 for injection site reaction or grade \leq 1 for any other toxicity related to the vaccines for the parameters used to assess levels of organ function required for eligibility (see Section [2](#)) after each vaccination in order to receive a subsequent vaccination. Patients will receive a diary card to record injections site reactions (see [Appendix B](#)).
If \geq grade 3 nonautoimmune toxicity attributable to the vaccines persists for $>$ 42 days, the patient will not receive further vaccine inoculations and will be removed from the protocol treatment and followed for resolution of toxicity and immune/survival endpoints.
- Patients who develop any \geq grade 3 autoimmunity, not related to a therapeutic response, will be removed from the protocol treatment and followed for resolution of toxicity and immune/survival endpoints.
- Patients who develop any grade 4 toxicity attributable to the vaccines will be removed from the protocol treatment and followed for resolution of toxicity and immune/survival endpoints.
- Dosing of the vaccines injections should be given on schedule every 3 weeks (Week 0, 3, and 6), and then bi-monthly (every 8 weeks) boosts for up to a year. In the event of conflicts, a +/- 1 week window is acceptable.
- For unrelated acute illnesses present at the time of a scheduled vaccination, dosing can be delayed until symptoms subside, or the subject may be withdrawn at the discretion of the Investigator; delays up to 4 weeks are considered acceptable in this setting.

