8.4.4 Safety Analysis

DLTs will be evaluated continuously in a dose level. An overall assessment of whether to de-escalate to the next dose level will be made at least 1 week after the last subject in the previous dose level has received their first injection. A dose level will be considered safe if $< 33\%$ of subjects treated at a dose level experience a DLT (i.e., 0 of 3, ≤ 1 of 6, ≤ 2 of 9, ≤ 3 of 10). Safety will be evaluated in 3 or 6 subjects at each dose level in the dose escalation component of the study. Safety will continue to be monitored among additional subjects treated at the MTD or HTD in the dose expansion component of the study. A subject will be considered evaluable for safety if treated with at least one injection. DLTs will be observed for 1 week.

Safety endpoints will be analyzed as summary statistics during treatment and/or as change scores from baseline assessments. AEs will be coded as defined in the Medical Dictionary for Regulatory Activities (MedDRA). All AEs will be recorded and tabulated following each treatment (vaccine injection). AEs will be recorded by severity, frequency, and relationship to the study intervention and will be presented by System Organ Class (SOC) designations and preferred term groupings. Information on each AE will include start date, stop date, severity, relationship, expectedness, outcome, and duration. Adverse events leading to premature discontinuation from the study intervention and serious treatment-emergent AEs will be presented either in a Table or a Listing.

In addition, overall safety will be assessed by descriptive analyses using tabulated frequencies of AEs by grade using CTCAE Version 5.0 within dose levels and for the overall study population in terms of treatment-emergent AEs, SAEs, and clinically significant changes in safety laboratory tests, physical examinations, ECGs, and vital signs.

The safety events listed in section [8.4.6.2](#) will trigger a temporary suspension of the study injections.:

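### The ±7-day dosing window lets dose 2 be given from day 14, inside the 3-week DLT period that follows dose 1

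*Combined protocol and SAP*

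**What the plan says.** Section 3.1.1 (Dose Limiting Toxicity) fixes the window: "For purposes of dose escalation the DLT evaluation period will be for 3 weeks following the first dose of drug". With listed exceptions, a DLT is "Any Grade 3 or greater toxicity that is possibly related to the vaccine". A subject who has one comes off protocol therapy.

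Sections 3.2, 3.3 and 11.1.5.3 place the first three doses at weeks 0, 3 and 6. Section 11.1.5.3 adds: "All study drug administration treatments should occur within ± 7 days of the planned visit date". Section 3.3 expects dosing on schedule and also offers a one-week window either way, but only for conflicts.

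Section 3.3 makes re-dosing depend on recovery from toxicity "after each vaccination in order to receive a subsequent vaccination". The section opens with a scope line: "Applies to events occurring outside of the DLT evaluation period".

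Section 8.4.4 (Safety Analysis) gives a different DLT period: "DLTs will be observed for 1 week". It also says that the de-escalation decision "will be made at least 1 week after the last subject in the previous dose level has received their first injection".

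**The concern.** The DLT period is meant to show what one dose of each of the three vaccines does before the subject is exposed again. Section 1.2.8 says the combination has not been tested in humans. If dose 2 is given on day 14, the last third of that period no longer describes a single dose. Three things follow for a subject dosed early.

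- **Counting.** A possibly related Grade 3 or higher event after dose 2, but within 21 days of dose 1, counts as a DLT under section 3.1.1. The dose decision turns on at most 1 against at least 2 of 6, so one subject's classification can change it.
- **Ascertainment.** If the week-3 visit moves to day 14 with the dose, the study calendar (section 3.5) schedules no visit or laboratory test for the remainder of days 14 to 21. The next scheduled visit is week 6, which is day 35 at the earliest.
- **Exposure.** The rule that removes a subject with a DLT cannot prevent dose 2 when a dose-1 DLT first appears after day 14.

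Of the primary endpoints, only the DLT component is touched.

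**Working it through.** The documents state no overlap figure, so there is none to reproduce first.

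**Day arithmetic.** Day 0 is taken as the actual first-dose date.

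- DLT period (3.1.1): 21 days. Planned dose 2 (11.1.5.3): day 21. Window (11.1.5.3): ±7 days.
- Earliest permitted dose 2: 21 − 7 = day 14.
- Overlap: 21 − 14 = 7 days, and 7/21 = 33%.
- Dose 2 on schedule at day 21: overlap 0.
- Under the 1-week text in 8.4.4, the period ends on day 7, before day 14: overlap 0.

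**Does another rule close the gap?** The recovery rule in 3.3 depends on resolved toxicity, not on elapsed time, so a subject who is well on day 14 passes it. The documents set no minimum interval between doses 1 and 2, and do not end DLT observation at dose 2.

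**Effect on the dose rule (illustration).** Assume that exactly one of six subjects is dosed on day 14, all events are ascertained, and dose 2 is no riskier than dose 1. Let p be the assumed 21-day DLT risk after one dose. Five subjects have risk p and the early subject has risk q:

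- No added risk: q = p.
- Constant hazard, with 21 + 7 = 28 dose-days instead of 21: q = 1 − (1 − p)^(28/21).
- All risk within 7 days of each injection: q = 1 − (1 − p)².

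The probability of meeting the de-escalation rule is

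P(≥2 of 6) = 1 − (1 − p)^5(1 − q) − [(1 − p)^5 q + 5p(1 − p)^4(1 − q)].

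| Assumed p | Case | q | P(≥2 of 6) |
|---|---|---|---|
| 0.10 | none early, or no added risk | 0.100 | 0.1143 |
| 0.10 | constant hazard | 0.131 | 0.1245 |
| 0.10 | all within 7 days | 0.190 | 0.1438 |
| 0.20 | none early, or no added risk | 0.200 | 0.3446 |
| 0.20 | constant hazard | 0.257 | 0.3681 |
| 0.20 | all within 7 days | 0.360 | 0.4102 |

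Worked line for p = 0.10 and q = 0.19: 1 − 0.59049 × 0.81 − (0.59049 × 0.19 + 0.32805 × 0.81) = 1 − 0.4783 − 0.3779 = 0.1438.

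Stopping early on 2 or more DLTs in the first 3 does not alter these figures, because that outcome already implies 2 or more of 6. Events missed on days 14 to 21 are not modelled and would lower them.

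**The case against.** The strongest reply is that the DLT rule stays well defined: the period is 3 weeks from dose 1, whatever is given within it, and counting an event after an early dose 2 is that rule at work. Extra counts lead toward de-escalation, which is cautious. This stands, and it is one reason the point is minor.

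Second, the loss of ascertainment is smaller than it looks. No subject has a scheduled visit or laboratory test between week 0 and week 3, and section 6.1 records a laboratory abnormality as an AE only under listed conditions. DLTs are monitored continuously (3.1.2), the team reviews each patient weekly (7.6.1), and dates are kept: "Information on each AE will include start date, stop date". This largely stands. What could be missed is mainly transient laboratory change without symptoms. An early visit does, however, give up the look at the end of the period that an on-schedule subject has on day 21.

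Third, the scope line in 3.3 cannot be used to weaken the recovery rule while leaving that section's own window intact. That is fair, but the gap does not depend on 3.3: section 11.1.5.3 allows early dosing without the conflict condition, and recovery by day 14 does not complete a 21-day observation.

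Fourth, the size is hypothetical. The documents give neither a DLT rate for the combination nor a frequency of early dosing, and the earlier trial of ETBX-011 alone reported no DLT (1.2.6.1, 11.1.2). At an assumed 5% risk, the same calculation goes from 3.3% to between 3.3% and 4.2%, with 3.6% under constant hazard. This stands as a limit on how much weight the figures can bear.

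Finally, under the 1-week text in 8.4.4 the overlap disappears. That is correct, but the text contradicts the DLT definition and needs correcting in any case. Once 3 weeks is confirmed, the overlap is real.

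**Conclusion.** The concern holds as a minor design point. Under the 3-week period, the plan permits 0 to 7 of 21 DLT days to follow a second dose. With one early subject in six, the illustrated rise in the chance of de-escalation is 0 to 3.0 percentage points at an assumed 10% risk (14.4 − 11.4) and 0 to 6.5 points at an assumed 20% (41.0 − 34.5). The upper ends require dosing on the earliest permitted day and all risk to fall within 7 days of an injection. The conclusion rests on section 3.1.1 governing the DLT period and on week 0 being the actual first-dose date. How often dose 2 would be given early is unknown. If it never is, nothing changes.

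**What to change.** In sections 11.1.5.3 and 3.3, for subjects in the dose-finding part (the first 3 to 6 at each dose level), set the dose-2 window to 0/+7 days, so not before day 21, and require the DLT assessment to be completed before the injection. Keep ±7 days for later doses. The overlap then becomes 0 of 21 days.

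In section 8.4.4, change both the 1-week DLT observation and the 1-week decision timing to 3 weeks. This takes section 3.1.1, where the DLT is defined, as the intended text.

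The cost is one clause in each of two sections and two corrected statements. Dose 2 loses a little scheduling flexibility in a few subjects. The earliest dose-level decision moves from 1 to 3 weeks after the last subject's first injection, a wait that the 3-week period in 3.1.1 already implies. Sample size and the number of visits do not change.

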11.1.6 Incompatibilities

The vaccines are administered as separate subcutaneous injections, with no known incompatibilities.

